9.2.1 Reporting of Adverse Events

The Sponsor will collect AEs until 30 days after administration of the last dose of study drug(s) or until the start of a new antitumor therapy, whichever occurs first. All AEs suspected to be related to study drug(s) must be followed after the time of therapy discontinuation until the event or its sequelae resolve or stabilize at an acceptable level to the Investigator and the Sponsor.

All AEs, including misuse, overdose and abuse must be recorded using medical terminology in the source document and the CRF. Whenever possible the Investigator will record the main diagnosis instead of the signs and symptoms normally included in the diagnoses.

Investigators must assess severity (grade) of the event following NCI-CTCAE v. 4 and assign relationship to each study drug; pursue and obtain information adequate both to determine the outcome and to assess whether it meets the criteria for classification as a SAE requiring immediate notification to PharmaMar or its designated representative. The Investigator must provide any relevant information as requested by the Sponsor in addition to that on the CRF.

Abnormal laboratory tests occurring during the study are AEs, but they should be collected only in the AE section of the CRF in some cases:

- Is associated with clinically significant symptoms, and/or
- Leads to a change in study dosing or discontinuation from the study, significant additional concomitant drug treatment or other therapy, and/or
- Leads to any of the outcomes included in the definition of a SAE.
- The test result is considered to be a clinically relevant by the Investigator.

Otherwise laboratory results should be reported in the corresponding section of the CRF (e.g. biochemistry, hematology).

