3.2 Secondary objectives

- To evaluate tumor response according to the international myeloma working group (IMWG) criteria.
- To assess duration of response (DR) and overall survival (OS).
- To assess efficacy in patients who undergo crossover from dexamethasone alone to plitidepsin and dexamethasone combination.
- To characterize and compare the safety profile on both arms in this population.
- To characterize the pharmacokinetics (PK) and pharmacokinetic/pharmacodynamic (PK/PD) relationship.

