Approximately 210 progression or death events would be needed in this trial to detect a HR of 0.625 in favor of the combination arm (equivalent to an increase of 60% in PFS, i.e., from 10 to 16 weeks, 12 to 19.2 weeks, 16 to 25.6 weeks) with 90% power and 1-sided 2.5% significance level. As a preliminary hypothesis, it is estimated that up to 250 randomized patients will be needed to achieve the 210 events in 24-30 months. For the calculation of the number of events needed, the target HR to be detected is 0.625, with 90% power and 2.5% unilateral significance level. This is equivalent to a minimum 60% increase in PFS, which has been considered statistically and clinically significant by the Sponsor.

An early futility analysis will be performed with the data collected when 40 patients in Arm A are evaluable for response. A response rate (IMWG criteria) of at least 30% (twelve or more responses by IRC review) will be taken as threshold for continuation of the study. A minimum response rate of 30% has been considered as clinically significant in this setting. This result will ensure that the lower limit of the exact binomial 95% Confidence Interval for the response rate will be greater than 15% (95% CI in case of 12 responses would be 16.6% - 46.5%).

However, the efficacy and safety information from all randomized patients in both arms at that time will be used by the independent data monitoring committee (IDMC) to provide the Sponsor with a recommendation for further study conduct.

The final PFS analysis will be performed when at least 210 progression or death events are observed.

An interim analysis of OS will be performed concomitantly with the final PFS analysis. In addition, a final analysis of OS will be performed when 80% of death events (approximately 200 death events) have occurred or 24 months after the inclusion of the last patient, whichever occurs first. At the interim OS analyses, the significance level determined by the O'Brien-Fleming (1) boundary with overall 2.5% 1-sided significance level will be used.

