12.2.2 Display of adverse events

Table 12.2.2.1 Summary of adverse events.

Category	Arm A	Arm B
	N (%)	N (%)
Patients with at least one AE regardless relationship		
Any treatment-related AE		
Any grade 3/4 AE		
Any grade 3/4 treatment-related AE		
Any SAE in DB		
Any treatment-related SAE		
Any grade 3/4 SAE		
Any grade 3/4 treatment-related SAE		
AEs leading to death		
AEs treatment-related leading to death		
AEs leading to dose delay		
AEs leading to dose reduction		
AEs leading to treatment discontinuation		
AEs treatment-related leading to treatment discontinuation		

Events with onset date after crossover will be excluded

Table 12.2.2.2 Evolution of myeloma-related AEs at baseline

	Arm A		Worst grade per patient						Total		
			0		1		...				
			N	%	N	%	N	%	N	%	
Baseline	Fatigue	Grade 0									
		Grade 1									
										
	Bone Pain	Grade 0									
		Grade 1									
										
	Myopathy	Grade 0									
		Grade 1									
										
										
	Arm B										
	Fatigue	Grade 0									
Grade 1											
.....											
Bone Pain	Grade 0										
	Grade 1										
										
Myopathy	Grade 0										
	Grade 1										
										

Events with onset date after crossover will be excluded

Table 12.2.2.3 Treatment-related adverse events. Worst grade by patient

SOC	Preferred Term	Arm A								Arm B							
		Grade 1		...	Grade 4		All*		Grade 1		...	Grade 4		All*			
		N	%	...	N	%	N	%	N	%	...	N	%	N	%		
Blood and lymphatic system disorders	Anemia NOS																
	Diarrhea NOS																
	...																
Cardiac disorders	Arrhythmia NOS																
	...																

(*) Any grade. Events with onset date after crossover will be excluded

Table 12.2.2.4 Treatment-related adverse events. Worst grade by cycle

SOC	Preferred Term	Arm A								Arm B							
		Grade 1		...	Grade 4		All*		Grade 1		...	Grade 4		All*			
		N	%	...	N	%	N	%	N	%	...	N	%	N	%		
Blood and lymphatic system disorders	Anemia NOS																
	Diarrhea NOS																
	...																
Cardiac disorders	Arrhythmia NOS																
	...																

* Any grade. Events with onset date after crossover will be excluded

Table 12.2.2.5 Treatment-related adverse events in “All Crossover Patients” population. Worst grade by patient

SOC	Preferred Term	Before crossover								After crossover*										
		Grade 1				Grade 4				Grade 1				Grade 4						
		N	%	N	%	N	%	N	%			
Blood and lymphatic system disorders	Anemia NOS																			

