12.7 Safety analysis in special subgroups

Table 12.7.1 Worst grade 3-4 by patient in special subgroups (Gender)

Events	Arm A						Arm B					
	Male			Female			Male			Female		
	N	Grade 3-4	%	N	Grade 3-4	%	N	Grade 3-4	%	N	Grade 3-4	%
Thrombocytopenia												
Neutropenia												
AP												
Total bilirubin												
AST												
ALT												
CPK												
Nausea												
Vomiting												
Fatigue												
Other*												

(*)Any treatment-related toxicity present in >=5% of patients in any group

Table 12.7.2 Worst grade 3-4 by patient in special subgroups (Age)

Events	Arm A						Arm B					
	<65 years old			...**			<65 years old			...**		
	N	Grade 3-4	%	N	Grade 3-4	%	N	Grade 3-4	%	N	Grade 3-4	%
Thrombocytopenia												
Neutropenia												
AP												
Total bilirubin												
AST												
ALT												
CPK												
Nausea												
Vomiting												
Fatigue												
Other*												

(*)Any treatment-related toxicity present in $\geq 5\%$ of patients in any group

(**) Age 65-74, Age 75-84, Age ≥ 85 . If there is a group of age with less than 5% of patients, it could be join with the previous/next group of age.

Table 12.7.3 Worst grade 3-4 by patient in special subgroups (BMI)

Events	Arm A						Arm B					
	<30			≥ 30			<30			≥ 30		
	N	Grade 3-4	%	N	Grade 3-4	%	N	Grade 3-4	%	N	Grade 3-4	%
Thrombocytopenia												
Neutropenia												
AP												
Total bilirubin												
AST												
ALT												
CPK												
Nausea												
Vomiting												
Fatigue												
Other*												

(*)Any treatment-related toxicity present in $\geq 5\%$ of patients in any group

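### The overview, by-patient and subgroup safety tables compare crude percentages over windows that may differ by arm; add a common-window incidence beside them

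*SAP*

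**What the plan says.** SAP 3.2 lists among the secondary objectives: "To characterize and compare the safety profile on both arms in this population". For AEs this is served mainly by Table 12.2.2.1 (any AE, grade 3/4 AE, SAE, AEs leading to death, dose delay, reduction or discontinuation), by Tables 12.2.2.3 and 12.2.2.6 (worst grade by patient), and by Tables 12.7.1 to 12.7.3 (sex, age, BMI). All report patients affected, as counts and percentages.

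Three rules set the period behind those percentages:

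- Treatment continues until progression or unacceptable toxicity, among other reasons (Protocol 5.2, SAP 2).
- AEs are collected to 30 days after the last dose, or to the start of a new antitumor therapy if earlier (Protocol 9.2.1).
- In Arm B, the footnote to Tables 12.2.2.1, 12.2.2.3 and 12.2.2.6 reads "Events with onset date after crossover will be excluded". A crossover patient's 30-day tail follows the combination phase (Protocol 5.1, SAP 8.2), so the dexamethasone phase has none.

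Tables 12.7.1 to 12.7.3 carry no crossover footnote. They choose their additional rows by a crude threshold: "Any treatment-related toxicity present in >=5% of patients in any group".

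On the expected PFS difference, SAP 5.2 says: "Approximately 210 progression or death events would be needed in this trial to detect a HR of 0.625 in favor of the combination arm", with medians going "from 10 to 16 weeks, 12 to 19.2 weeks, 16 to 25.6 weeks". No expected treatment duration or AE observation time is stated.

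**The concern.** A crude percentage depends on the event rate and on how long each patient is watched. If Arm A is watched longer because its patients progress later, an event that keeps occurring at the same rate in both arms will affect a larger share of Arm A. The efficacy benefit would then be read partly as toxicity. If Arm A instead stops early for toxicity, the crude percentage would understate its event rate. The SAP checks symmetry of assessment timing for efficacy (6.1.2, 11.3.4.7) but has no matching step for the AE summaries.

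**Working it through.** **The plan's own figures.** 1/0.625 = 1.6, which gives 10 × 1.6 = 16, 12 × 1.6 = 19.2 and 16 × 1.6 = 25.6 weeks, as stated. With 90% power, one-sided 2.5% and 2:1 allocation, the Schoenfeld formula gives (1.960 + 1.282)² / [(2/3)(1/3)(ln 0.625)²] = 214.04, so 215 events. The plan's 210 give 89.4% power. The 1.6 ratio is therefore the design alternative for PFS.

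**Assumptions for the windows.** Treatment time is exponential and ends only at progression. The 30-day tail (30/7 = 4.29 weeks) is complete. A fraction f of Arm B patients who progress at or after week 8 cross over at once and lose the tail; f = 0, 50% or 80% is assumed, since the documents give no figure.

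- Mean window A = 1.6 m / ln 2 + 4.29, where m is the Arm B median.
- Mean window B = m / ln 2 + 4.29 × (1 − f c), where c = 2^(−8/m) is the share of Arm B still on treatment at week 8.

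For m = 12: A = 27.70 + 4.29 = 31.99 weeks; c = 0.63; B = 21.60 weeks at f = 0 and 17.31 + 4.29 × (1 − 0.8 × 0.63) = 19.44 at f = 80%.

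| Arm B median (weeks) | Ratio A/B, f = 0 | f = 50% | f = 80% |
|---|---|---|---|
| 10 | 1.46 | 1.57 | 1.63 |
| 12 | 1.48 | 1.58 | 1.65 |
| 16 | 1.51 | 1.59 | 1.65 |

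**Effect on a crude percentage.** With an equal constant hazard, simulation over these nine scenarios gives Arm A 26.8% to 29.5% when Arm B shows 20%, and 38.6% to 42.0% when Arm B shows 30%. A closed form for exponential windows of ratio r, odds in A = r × odds in B, agrees: r = 1.5 gives 0.375/1.375 = 27.3%, and r = 1.6 gives 0.40/1.40 = 28.6%.

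**When the effect shrinks.**

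- HR = 1: the ratio is 1.0 without crossover. At m = 12 and f = 80% the lost tail alone gives 21.60/19.44 = 1.11.
- If 10%, 20% or 30% of Arm A stop for toxicity before progression (assumed, none in Arm B), the ratio on treatment time alone is 1.6 × 0.9 = 1.44, 1.6 × 0.8 = 1.28 and 1.6 × 0.7 = 1.12.
- If the hazard is confined to the first 4 weeks, 20% in Arm B corresponds to 20.6% to 21.0% in Arm A without a tail. With a full tail everyone is observed past week 4 and the shares are equal.

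**Check on an 8-week window.** Mean time observed up to week 8 is 4.29 + mean treatment time × (1 − 2^(−3.71/median)). At 12/19.2 weeks this is 7.63 weeks in B and 7.76 in A, a ratio of 1.02; over the three median pairs the difference is 1% to 2%.

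**Check on a rate per patient-time.** Take identical risk in both arms, 20%, confined to the first 4 weeks. Mean time to those events is 1.93 weeks. At m = 12 without crossover, mean time at risk is 0.2 × 1.93 + 0.8 × 31.99 = 25.98 weeks in A and 0.2 × 1.93 + 0.8 × 21.60 = 17.67 in B. The rate ratio A/B is 17.67/25.98 = 0.68 (0.67 to 0.69 over the three medians), although the risks are equal.

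**The case against.** A reader might infer that no safety table uses a common window or allows for exposure. The SAP does not support that. Table 12.4.4.3 sets cycle 1 laboratory abnormalities side by side by arm, with cycles evaluated as denominator. AE terms have by-cycle tables (12.2.2.4, 12.2.2.7), as do laboratory grades (12.4.1.2, 12.4.2.2, 12.4.3.2). Delays, omissions and reductions are counted per susceptible cycle (12.1.2 to 12.1.4). Table 10.2.5 gives discontinuation reasons by last cycle, and Table 12.1.1.1 gives time on treatment by arm. This stands and narrows the point to SAEs, fatal AEs, the overview any-AE and grade 3/4 rows, and section 12.7. The by-cycle AE tables also do not state their denominator.

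A reader might also infer that the plan expects Arm A to be observed 1.5 to 1.6 times as long. It does not say so: 1.6 is the PFS ratio under the alternative, and treatment can also end for toxicity, refusal, prolonged delay or more than two dose reductions. Patients who start new therapy or die lose part of the tail in either arm.

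Finally, the safety analysis is descriptive, by arm, and the AE tables carry no test. The share of patients affected over a course of treatment is a legitimate quantity. That stands too, and it is why the crude percentages should stay. Since comparison is a stated objective, the two columns will still be read against each other.

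**Conclusion.** The point holds as a conditional one. Under the design alternative, with treatment ending mainly at progression and an equal persistent hazard, the mean window ratio is about 1.5 to 1.65, and 20% in Arm B would appear as about 27% to 30% in Arm A. These are model results under assumed crossover fractions, not planned or observed exposures. It would go too far to say that equal toxicity will be shown as an excess on plitidepsin: the ratio is about 1.0 if HR = 1, is smaller if Arm A stops early for toxicity, and early-onset events show little excess. For section 12.7 the figures apply only if Arm B is cut at crossover there as well, which the tables do not say. The primary analysis is unaffected. This is a cheap improvement.

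**What to change.** Keep the crude N (%) in Tables 12.2.2.1, 12.2.2.3, 12.2.2.6 and 12.7.1 to 12.7.3, and add beside it:

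1. The incidence of events with onset within 8 weeks of randomization, a period before crossover is allowed. Alternatively, give the cumulative incidence of the first event, truncated at a common time, with Arm B censored at the first combination dose and death as a competing event.
2. As a supplement only, first events per 100 patient-months with 95% CI. Label it as assuming a constant rate. Do not use it alone for the between-arm statement, because it favours the longer-exposed arm for early-onset events (0.67 to 0.69 in the check above).

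State the denominator (cycles observed) of Tables 12.2.2.4 and 12.2.2.7. State whether Tables 12.7.1 to 12.7.3 exclude events after crossover. Say in SAP 7.1 that crude percentages are to be read together with time on treatment by arm (Table 12.1.1.1).

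The cost is SAP wording, some programming and longer tables. Dosing, AE, follow-up and death data are already collected (SAP section 13 listings).

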12.3.1 Serious Adverse Events

Listing 12.3.1.1 SAEs

Arm	Patient id.	Cycle	Preferred term code	Adverse event reported (verbatim)	Status	Grade	Relationship	Onset date	Resolved date	Action	Serious Criteria
...											

SAEs narratives of pharmacovigilance DB will be provided by the pharmacovigilance department.

12.3.2 Deaths

Table 12.3.2.1 Cause of death

Reason*	Arm A		Arm B	
	N	%	N	%
Malignant disease				
Treatment-related adverse event				
Other				
Total				

(*) Denominator=Number of patients who died

Listing 12.3.2.2 Deaths

Arm	Patient id.	Death date	Cause	Comments	Autopsy	Autopsy report available	Number of cycles administered	Last infusion date	Time on treatment*	Time from Last dose**
...										

(*)Time on treatment: defined as last infusion date plus 30 days, or date of death or subsequent therapy (whichever comes first) minus first infusion date. (**)Time from last dose defined as death date minus last infusion date.

Listing 12.3.2.3 Deaths due to AEs

Arm	Patient id.	Cycle	Preferred term code	Adverse event reported (verbatim)	Grade	Relationship	Onset date	Resolved date	Action
...									

* AEs with Seriousness=Death

12.4 Clinical laboratory evaluation

12.4.1 Hematological abnormalities

Hematological toxicities classified according to the NCI-CTC will be calculated for all cycles. The worst grade reached by each patient during treatment will be also calculated.

If serious toxicities happen, special follow-up, with descriptives and graphs (boxplots, line plots) will be made to find out the pattern of thrombocytopenia and neutropenia within and between the different cycles.

Table 12.4.1.1 Hematological abnormalities during treatment, worst grade per patient

	Arm A								Arm B													
	N		Grade 1		...		Grade 4		All*		N		Grade 1		...		Grade 4		All*			
	N	%	N	%	N	%	N	%	N	%	N	%	N	%	N	%	N	%	N	%		
Leukopenia																						
Anemia																						
Thrombocytopenia																						
Neutropenia																						
Lymphopenia																						

(*) Any grade. Events with onset date after crossover will be excluded

Table 12.4.1.2 Hematological abnormalities during treatment, worst grade per cycle

	Arm A								Arm B													
	N		Grade 1		...		Grade 4		All*		N		Grade 1		...		Grade 4		All*			
	N	%	N	%	N	%	N	%	N	%	N	%	N	%	N	%	N	%	N	%		
Leukopenia																						
Anemia																						
Thrombocytopenia																						
Neutropenia																						
Lymphopenia																						

(*) Any grade. Events with onset date after crossover will be excluded

Table 12.4.1.3 Hematological abnormalities in during treatment in the “All Crossover Patients” population, worst grade per patient

	Arm B, before crossover								Arm B, after crossover to Arm A													
	N		Grade 1		...		Grade 4		All*		N		Grade 1		...		Grade 4		All*			
	N	%	N	%	N	%	N	%	N	%	N	%	N	%	N	%	N	%	N	%		
Leukopenia																						
Anemia																						
Thrombocytopenia																						
Neutropenia																						
Lymphopenia																						

(*) Any grade

Listing 12.4.1.4 Grade 3-4 hematological abnormalities during treatment. Worst grade per patient

Arm	Patient id.	Test	Grade
...			

Events with onset date after crossover will be excluded

Listing 12.4.1.5 Grade 3-4 hematological abnormalities during treatment. Worst grade per cycle

Arm	Patient id.	Test	Grade
...			

Events with onset date after crossover will be excluded

Listing 12.4.1.6 Hematological tests not assessed at any treatment visit per patient

Arm	Patient id.	Lab. test
...		

Listing 12.4.1.7 Hematological tests not assessed by patient and cycle

Arm	Patient id.	Cycle	Lab. test
...			

Table 12.4.1.8 Platelets and RBC transfusions during the study

		Platelets (Units)		Red Blood Cells (Units)	
		Arm A	Arm B	Arm A	Arm B
		N(%)	N(%)	N(%)	N(%)
Platelets (Units)	0 transfusions				
	1 transfusion				
	...				
	Median (range)				
Red Blood Cells (Units)	0 transfusions				
	1 transfusion				
	...				
	Median (range)				

Events with onset date after crossover will be excluded

These tables will be complemented with plots for the median nadir of neutrophils (Figure 12.4.1.9), platelets count (Figure 12.4.1.10) and hemoglobin values (Figure 12.4.1.11) by cycle along the treatment. Furthermore, if appropriate, graphs of the intercycle time course of neutropenia and thrombocytopenia will be provided. Eventually, graphs comparing the time course during the first and second cycle will be created.

Listing 12.4.1.12 Grade 3-4 hematological abnormalities during treatment in the “All Crossover Patients” population. Worst grade per patient

Arm	Patient id.	Test	Grade
...			

Listing 12.4.1.13 Grade 3-4 hematological abnormalities during treatment in the “All Crossover Patients” population. Worst grade per cycle

Arm	Patient id.	Test	Grade
...			

12.4.2 Biochemical abnormalities

Grades of liver toxicity and intercycle pattern of creatinine, CPK, bilirubin, transaminases increase and alkaline phosphatase increase during a cycle will be calculated, as it is explained in the corresponding section for hematological toxicities.

Table 12.4.2.1 Biochemical abnormalities during treatment, worst grade per patient

	Arm A								Arm B													
	N		Grade 1		...		Grade 4		All*		N		Grade 1		...		Grade 4		All*			
	N	%	N	%	N	%	N	%	N	%	N	%	N	%	N	%	N	%	N	%		
AST increase																						
ALT increase																						
Total bilirubin increase																						
AP increase																						
Creatinine increase																						
CPK increase																						

(*) Any grade. Events with onset date after crossover will be excluded

Table 12.4.2.2 Biochemical abnormalities during treatment, worst grade per cycle

	Arm A								Arm B													
	N		Grade 1		...		Grade 4		All*		N		Grade 1		...		Grade 4		All*			
	N	%	N	%	N	%	N	%	N	%	N	%	N	%	N	%	N	%	N	%		
AST increase																						
ALT increase																						
Total bilirubin increase																						
AP increase																						
Creatinine increase																						
CPK increase																						

(*) Any grade. Events with onset date after crossover will be excluded

Table 12.4.2.3 Biochemical abnormalities during treatment in the “All Crossover Patients” population, worst grade per patient

	Arm B, before crossover								Arm B, after crossover to Arm A													
	N		Grade 1		...		Grade 4		All*		N		Grade 1		...		Grade 4		All*			
	N	%	N	%	N	%	N	%	N	%	N	%	N	%	N	%	N	%	N	%		
AST increase																						
ALT increase																						
Total bilirubin increase																						
AP increase																						
Creatinine increase																						
CPK increase																						

(*) Any grade

Listing 12.4.2.4 Grade 3-4 biochemical abnormalities during treatment. Worst grade per patient

Arm	Patient id.	Test	Grade
...			

Events with onset date after crossover will be excluded

Listing 12.4.2.5 Grade 3-4 biochemical abnormalities during treatment. Worst grade per cycle

Arm	Patient id.	Cycle	Test	Grade
...				

Events with onset date after crossover will be excluded

Listing 12.4.2.6 Biochemical tests not assessed at any treatment visit by patient

Arm	Patient id.	Lab. test
...		

Listing 12.4.2.7 Biochemical tests not assessed by patient and cycle

Arm	Patient id.	Cycle	Lab. test
...			

These tables will be complemented with plots for the median peak of ALT (Figure12.4.2.8), AST (Figure12.4.2.9) and CPK values (Figure12.4.2.10) by cycle along the treatment. If appropriate, graphs of the intercycle time course of ALT, AST and CPK will be provided.

Listing 12.4.2.11 Grade 3-4 biochemical abnormalities during treatment in the “All Crossover Patients” population. Worst grade per patient

Arm	Patient id.	Test	Grade
...			

Listing 12.4.2.12 Grade 3-4 biochemical abnormalities during treatment in the “All Crossover Patients” population. Worst grade per cycle

Arm	Patient id.	Test	Grade
...			

